Original Protocol	22-SEP-2020	Not applicable

PROTOCOL AMENDMENT SUMMARY OF CHANGES

Amendment: 04

Overall Rationale for the Amendment:

To add the option of an extension study.

Summary of Changes Table

Section Number and Name	Description of Change	Brief Rationale
Primary Reason for Amendment		
Section 6.7, Intervention After the End of the Study	Added extension study language for intervention after the end of the study.	To address a strategy change by providing an option for participants to roll over into an extension study.

Section Number and Name	Description of Change	Brief Rationale
Additional Changes		
Title Page	Added NCT number.	For completeness.
	Added EU CT number.	See rationale above.
Section 4.4, Beginning and End of Study Definition	Added definition of when the overall study ends for purposes of analysis and reporting.	To align with the EU CTR.
	Added definition of local start of the study for EEA countries.	See rationale above about the EU CTR.
Section 8.4.4, Regulatory Reporting Requirements for SAE	Added a statement describing how to report SUSARs.	Refer to Section 4.4 rationale about the EU CTR.
Section 9.1, Statistical Analysis Plan Summary	Specified that no formal interim analysis is planned.	Interim analyses have been performed but were not formally planned.
Section 9.5.2, Safety Analysis Population	Removed reference to Section 9.6 for details on handling missing data for safety analyses.	To correct an error.
Section 9.7, Interim Analyses	Specified that no formal interim analyses are planned.	Refer to Section 9.1 rationale.
Section 9.7.1, Efficacy Interim Analysis	Specified that no formal interim analysis for efficacy is planned.	Refer to Section 9.1 rationale.
	Updated timing of final analysis from 24 months to approximately 36 months.	To align with the end of the study.
Section 10.1.3, Data Protection	Added text regarding Sponsor's EU-approved Binding Corporate Rules.	Refer to Section 4.4 rationale about the EU CTR.

Section Number and Name	Description of Change	Brief Rationale
Section 10.1.5, Compliance With Study Registration and Results Posting Requirements	Updated referenced EU regulation and added a submission website link.	Refer to Section 4.4 rationale about the EU CTR.
Section 10.1.6, Compliance with Law, Audit, and Debarment	Added text for investigators located in countries with serious breach reporting requirements.	Refer to Section 4.4 rationale about the EU CTR.

1 PROTOCOL SUMMARY

1.1 Synopsis

Protocol Title: A Phase 2, Single-arm, Open-label Clinical Trial of Pembrolizumab Plus Lenvatinib in Participants with First-line Advanced/Metastatic Non-clear Cell Renal Cell Carcinoma (nccRCC) (KEYNOTE-B61)

Short Title: Pembro + Lenva for 1L nccRCC

Acronym: KEYNOTE-B61

Hypotheses, Objectives, and Endpoints:

In male or female participants at least 18 years of age with previously untreated histologically confirmed advanced/metastatic nccRCC:

Primary Objectives	Primary Endpoints
- To evaluate the ORR of pembrolizumab + lenvatinib per RECIST 1.1 by blinded independent central review (BICR)	- Objective response (OR): a confirmed complete response (CR) or partial response (PR)
Secondary Objectives	Secondary Endpoints
- To evaluate the DOR of pembrolizumab + lenvatinib in participants with a confirmed CR or PR per RECIST 1.1 by BICR	- DOR: the time from first documented evidence of CR or PR until disease progression or death due to any cause, whichever occurs first
- To evaluate PFS per RECIST 1.1 by BICR in participants receiving pembrolizumab + lenvatinib	- PFS: the time from first dose to the first documented PD or death from any cause, whichever occurs first
- To evaluate the overall survival (OS) of participants receiving pembrolizumab + lenvatinib	- OS: the time from first dose until death from any cause
- To evaluate the CBR of pembrolizumab + lenvatinib per RECIST 1.1 by BICR	- Clinical benefit: a confirmed CR, PR, or stable disease (SD) for at least 6 months
- To evaluate the DCR of pembrolizumab + lenvatinib per RECIST 1.1 by BICR	- Disease control: a confirmed CR, PR or SD
- To evaluate the safety of pembrolizumab + lenvatinib	- Adverse events (AEs) - Discontinuations due to AEs

Overall Design:

Study Phase	Phase 2
Primary Purpose	Treatment
Indication	Previously untreated advanced or metastatic nccRCC
Population	Participants with previously untreated advanced or metastatic nccRCC
Study Type	Interventional
Intervention Model	Single Group This is a multisite study.
Type of Control	No Treatment Control
Study Blinding	Unblinded Open-label
Blinding Roles	Outcomes Assessor
Estimated Duration of Study	The Sponsor estimates that the study will require approximately 5 years from the time the first participant (or their legally acceptable representative) provides documented informed consent until the last participant's last study-related contact.

Number of Participants:

Approximately 152 participants will be enrolled in the study.

Intervention Groups and Duration:

Intervention Groups	

Intervention Group Name	Drug	Dose Strength	Dose Frequency	Route of Administration	Regimen/ Treatment Period	Use	

Pembrolizumab + Lenvatinib	Pembro-lizumab	400 mg	Q6W	IV	Up to 18 infusions, progressive disease or discontinuation	Experi-mental	

Lenvatinib	20 mg	QD	Oral	Until progressive disease or discontinuation	Experi-mental	

	Intervention Group Name	Drug	Dose Strength	Dose Frequency	Route of Administration	Regimen/ Treatment Period	Use	Pembrolizumab + Lenvatinib	Pembro-lizumab	400 mg	Q6W	IV	Up to 18 infusions, progressive disease or discontinuation	Experi-mental	Lenvatinib	20 mg	QD	Oral	Until progressive disease or discontinuation	Experi-mental
	Intervention Group Name	Drug	Dose Strength	Dose Frequency	Route of Administration	Regimen/ Treatment Period	Use														
	Pembrolizumab + Lenvatinib	Pembro-lizumab	400 mg	Q6W	IV	Up to 18 infusions, progressive disease or discontinuation	Experi-mental														
		Lenvatinib	20 mg	QD	Oral	Until progressive disease or discontinuation	Experi-mental														
IV=intravenous; Q6W=every 6 weeks; QD=every day.																					
Other current or former names or aliases for study interventions are as follows: Pembrolizumab: KEYTRUDA®, MK-3475, lambrolizumab Lenvatinib: LENVIMA®, Kisplyx, MK-7902, E7080																					
Total Number of Intervention Groups/ Arms	1																				
Duration of Participation	
Each participant will participate in the study from the time the participant provides documented informed consent through the final protocol-specified contact.
 
After a screening phase of up to 28 days, each participant will be assigned to receive study intervention. Study intervention with pembrolizumab will continue for up to 18 administrations (approximately 2 years) or until a discontinuation criterion is met. Study intervention with lenvatinib may continue beyond 2 years until a discontinuation criterion is met. Participants who stop study intervention after receiving 18 administrations of pembrolizumab for reasons other than disease progression or intolerability, or participants who attain a complete response and stop study intervention may be eligible for up to 9 additional administrations of pembrolizumab (approximately 1 year) upon experiencing disease progression (Section 8.10.3).
 
After the end of treatment, each participant will be followed for the occurrence of adverse events and spontaneously reported pregnancy as described under Section 8.4.
																				

	Participants who discontinue for reasons other than radiographic disease progression will have post-treatment follow-up imaging for disease status until disease progression is documented radiographically per RECIST 1.1, the start of a new anti-cancer treatment, withdrawal of consent, pregnancy, death, or loss to follow-up. All participants will be followed by telephone for overall survival until death, withdrawal of consent, or the end of the study.
--	---

Study Governance Committees:

Steering Committee	No
Executive Oversight Committee	No
Data Monitoring Committee	No
Clinical Adjudication Committee	No

[figure not shown]
Study Accepts Healthy Volunteers: No

A list of abbreviations used in this document can be found in Appendix 9.

1.2 Schema

The study design is depicted in [Figure 1](#).

Figure 1 Study Schema

1L=first-line; AJCC=American Joint Committee on Cancer; DC=discontinuation; IMDC=International Metastatic RCC Database Consortium; IV=intravenous; KPS=Karnofsky Performance Status; nccRCC=non-clear cell renal cell carcinoma; PO=per oral; PD=progressive disease; Q6W=every 6 weeks; QD=every day.

1.3 Schedule of Activities

1.3.1 Initial Treatment Phase

Table 1 Schedule of Activities – Initial Treatment Phase

Trial Period	Screening	Initial Treatment Phase Cycle = 42 Days														EOT	Posttreatment			Notes			
		Safety FU						Efficacy FU		Survival FU													
Visit Timing/ Cycle Number		1						2		3		4		5 to 18		>18		At D/C	30 days after last dose	Per Imaging Schedule	Q12W	All procedures/ assessments are to be performed prior to dosing unless otherwise indicated.	
Cycle Day		1	8	15	22	36	1	22	1	22	1	22	1	22	1	22							
Scheduling Window (days)	-28 to -1	+3	±3	±3	±3	±3	±3	±3	±3	±3	±3	±3	±3	±3	±3	±3		+7	±7	±14			
Administrative Procedures																							
Informed Consent	X																						Informed consent must be obtained prior to any protocol-specific procedures. If the investigator plans to treat beyond disease progression, additional consent is required.
Inclusion/ Exclusion Criteria	X																						
Participant Identification Card	X	X*																					*Update with allocation number from IRT.
nccRCC Disease History	X																						
Demographics and Medical History	X																						Medical history includes substance usage (drugs, alcohol, tobacco and caffeine), family history of premature CV disease, and surgical history.

Trial Period	Screening	Initial Treatment Phase Cycle = 42 Days														EOT	Posttreatment			Notes	
								Safety FU	Efficacy FU	Survival FU											
Visit Timing/ Cycle Number		1					2		3		4		5 to 18		>18		At D/C	30 days after last dose	Per Imaging Schedule	Q12W	All procedures/ assessments are to be performed prior to dosing unless otherwise indicated.
Cycle Day		1	8	15	22	36	1	22	1	22	1	22	1	22	1	22					
Scheduling Window (days)	-28 to -1	+3	±3	±3	±3	±3	±3	±3	±3	±3	±3	±3	±3	±3	±3	±3		+7	±7	±14	
Tumor Imaging and Efficacy Assessments																					
Imaging of chest/ abdomen/ pelvis and Response Assessment	X	

																			

Trial Period	Screening	Initial Treatment Phase Cycle = 42 Days														EOT	Posttreatment			Notes
																	Safety FU	Efficacy FU	Survival FU	
Visit Timing/ Cycle Number		1				2		3		4		5 to 18		>18		At D/C	30 days after last dose	Per Imaging Schedule	Q12W	All procedures/ assessments are to be performed prior to dosing unless otherwise indicated.
Cycle Day		1	8	15	22	36	1	22	1	22	1	22	1	22	1	22				
Scheduling Window (days)	-28 to -1	+3	±3	±3	±3	±3	±3	±3	±3	±3	±3	±3	±3	±3	±3	±3	+7	±7	±14	
Bone Scan	X																			Perform a screening bone scan in all participants. After allocation, only continue bone scans if participant's scan at Screening was positive. The schedule for bone scans is at Week 18 (126 ± 7 days); Q12W (84 ± 7 days) until Week 54; then Q24W (168 ± 7 days) thereafter. Perform for participants at time of CR if positive at baseline. Schedule should follow calendar days and not be adjusted for delays in treatment.
Brain Scan	X*																			*Perform at Screening ONLY for participants with previously documented brain metastases (to confirm stability) or who are clinically symptomatic. Brain scans will be performed as clinically indicated and to confirm a CR in participants with brain metastasis at baseline.

31-OCT-2024

Trial Period	Screening	Initial Treatment Phase Cycle = 42 Days														EOT	Posttreatment			Notes	
																	Safety FU	Efficacy FU	Survival FU		
Visit Timing/ Cycle Number		1					2		3		4		5 to 18		>18		At D/C	30 days after last dose	Per Imaging Schedule	Q12W	All procedures/assessments are to be performed prior to dosing unless otherwise indicated.
Cycle Day		1	8	15	22	36	1	22	1	22	1	22	1	22	1	22					
Scheduling Window (days)	-28 to -1	+3	±3	±3	±3	±3	±3	±3	±3	±3	±3	±3	±3	±3	±3	±3		+7	±7	±14	
12-lead ECG	X	X			X		X			X*		X*		X*		X		X			*After Cycle 2, repeat ECG every other cycle (eg, C4, C6, C8, C10, etc.). For high-risk participants (Section 8.3.3), conduct ECG monitoring every cycle. If lenvatinib is discontinued, ECGs are only required at the EOT and Safety Follow-up visits.
KPS	X																				At screening, perform within 10 days prior to first dose of study intervention.
ECOG Performance Status	X	X					X		X		X		X		X		X	X			At screening, perform within 10 days prior to first dose of study intervention.

MK-3475-B61-04 FINAL PROTOCOL

Trial Period	Screening	Initial Treatment Phase Cycle = 42 Days														EOT	Posttreatment			Notes	
																	Safety FU	Efficacy FU	Survival FU		
Visit Timing/ Cycle Number		1					2		3		4		5 to 18		>18		At D/C	30 days after last dose	Per Imaging Schedule	Q12W	All procedures/ assessments are to be performed prior to dosing unless otherwise indicated.
Cycle Day		1	8	15	22	36	1	22	1	22	1	22	1	22	1	22					
Scheduling Window (days)	-28 to -1	+3	±3	±3	±3	±3	±3	±3	±3	±3	±3	±3	±3	±3	±3	±3		+7	±7	±14	
Urine Dipstick Testing (or Urinalysis) for Protein	X	X	X	X	X	X	X	X	X	X	X	X	X	X	X	X					Urinalysis as clinically indicated. See Section 6.6.2.2 for guidance on testing frequency in cases of elevated protein. Participants with proteinuria ≥2+ (≥100 mg/dL) at screening will undergo 24-hour urine collection for quantitative assessment of proteinuria.
HIV, Hepatitis B, Hepatitis C	X*																				*Only if mandated by local health authority. Refer to Appendix 7 for country-specific requirements.
Hematology	X	X		X			X		X		X		X		X		X	X			At screening, perform within 10 days prior to first dose of study intervention.
Chemistry	X	X		X			X		X		X		X		X		X	X			
Lipase and Amylase	X	X		X			X		X		X		X		X		X	X			

Trial Period	Screening	Initial Treatment Phase Cycle = 42 Days														EOT	Posttreatment			Notes			
		1						2		3		4		5 to 18			>18		Safety FU		Efficacy FU	Survival FU	
Visit Timing/ Cycle Number		1						2		3		4		5 to 18		>18		At D/C	30 days after last dose	Per Imaging Schedule	Q12W	All procedures/ assessments are to be performed prior to dosing unless otherwise indicated.	
Cycle Day		1	8	15	22	36	1	22	1	22	1	22	1	22	1	22							
Scheduling Window (days)	-28 to -1	+3	±3	±3	±3	±3	±3	±3	±3	±3	±3	±3	±3	±3	±3	±3		+7	±7	±14			
PT/INR and aPTT or PTT	X																					At screening, perform within 10 days prior to first dose of study intervention. PTT is acceptable if aPTT cannot be determined. Perform additional testing as clinically indicated for participants taking anticoagulants.	
T3 or FT3, FT4, TSH	X	X					X		X		X		X		X		X	X				At screening, perform within 10 days prior to first dose of study intervention.	
Biomarkers																							
Blood for Genetic Analysis		X																				This sample should be drawn for planned analysis of the association between genetic variants in DNA and drug response. This sample will not be collected at that site if there is either a local law or regulation prohibiting collection, or if the IRB/IEC does not approve the collection of the sample for these purposes.	

Trial Period	Screening	Initial Treatment Phase Cycle = 42 Days														EOT	Posttreatment			Notes			
		1						2		3		4		5 to 18			>18		Safety FU		Efficacy FU	Survival FU	
Visit Timing/ Cycle Number		1						2		3		4		5 to 18		>18		At D/C	30 days after last dose	Per Imaging Schedule	Q12W	All procedures/ assessments are to be performed prior to dosing unless otherwise indicated.	
Cycle Day		1	8	15	22	36	1	22	1	22	1	22	1	22	1	22							
Scheduling Window (days)	-28 to -1	+3	±3	±3	±3	±3	±3	±3	±3	±3	±3	±3	±3	±3	±3	±3		+7	±7	±14			
Blood for Serum Biomarkers		X		X			X		X								X						
Blood for ctDNA Analysis		X					X		X		X*		X*		X*		X						* After C3D1, collect blood for ctDNA at D1 of every cycle (C4, C5, C6, etc.) up until and at C10. After C10D1, collect D1 of every other cycle (C12, C14, C16, etc.). Collect at EOT.
Archival or Newly Obtained Tumor Tissue Sample Collection	X																						Tumor tissue (archival or newly acquired core or excisional biopsy) will be obtained and submitted at screening. Tumor blocks are preferred over cut slides.

AE=adverse event; aPTT=activated PTT; C=Cycle; ctDNA=circulating tumor DNA; CR=complete response; CV=cardiovascular; D=Day; DBP=diastolic blood pressure; D/C=discontinuation; DNA=deoxyribonucleic acid; ECG=electrocardiogram; ECI=event of clinical interest; ECHO=echocardiogram; ECOG=Eastern Cooperative Oncology Group; EOT=end-of-treatment; FT3=free T3; FT4=free thyroxine; FU=follow-up; hCG=human chorionic gonadotropin; HIV=human immunodeficiency virus; HR=heart rate; IEC=independent ethics committee; INR=international normalized ratio; IRB=institutional review board; IRT=interactive response technology; KPS=Karnofsky performance status; MUGA=multiple gated acquisition scan; nccRCC=non-clear cell renal cell carcinoma; PT=prothrombin time; PTT=partial thromboplastin time; Q6W=every 6 weeks; Q12W=every 12 weeks; Q24W=every 24 weeks; RR=respiratory rate; SAE=serious adverse event; SBP=systolic blood pressure; T3=triiodothyronine; TSH=thyroid-stimulating hormone; WOCBP=woman of childbearing potential.

[figure not shown]
[figure not shown]
1.3.2 Translational Oncology Research

Table 2 Schedule of Activities – Additional Biomarker Collections From Select Sites

Trial Period	Screen- ing	Initial Treatment Phase Cycle = 42 Days														EOT	Posttreatment			Notes	
																	Safety FU	Efficacy FU	Survival FU		
Visit Timing/ Cycle Number		1					2		3		4		5 to 18		>18		At D/C	30 days after last dose	Per Imaging Schedule	Q12W	At selected TOR sites, all samples will be collected as indicated in the Schedule of Activities from all participants at these sites. See Procedure Manual for details of selected sites.
Cycle Day		1	8	15	22	36	1	22	1	22	1	22	1	22	1	22					
Scheduling Window (days)	-28 to -1	+ 3	±3	±3	±3	±3	±3	±3	±3	±3	±3	±3	±3	±3	±3	±3		+7	±7	±14	
Biomarker Sample Collection																					
Blood for RNA Analysis		X		X			X										X				
Blood for PBMC		X		X			X										X				
D/C=discontinuation; EOT=end-of-treatment; FU=follow-up; PBMC=peripheral blood mononuclear cells; Q12W=every 12 weeks; RNA=ribonucleic acid; TOR=translational oncology research.																					

1.3.3 Second Course Treatment Phase

Table 3 Schedule of Activities – Second Course Treatment Phase

Trial Period	Second Course Treatment Phase Cycle = 42 days						EOT	Posttreatment			Notes
Visit Timing/ Cycle Number	1		2		3 to 9			Safety FU	Efficacy FU	Survival FU	
Cycle Day	1	22	1	22	1	22	At D/C	30 days after D/C	Per Imaging Schedule	Q12W	All procedures/ assessments are to be performed prior to dosing unless otherwise indicated.
Scheduling Window (days)	+3	±3	±3	±3	±3	±3	+7	±7	±7	±14	
Administrative Procedures											
Informed consent	X										Obtain prior to initiating Second Course treatment. If the investigator plans to treat beyond disease progression, additional consent is required.
Second Course Eligibility Criteria	X										The Second Course eligibility criteria must be satisfied, and all safety parameters listed in the inclusion criteria and none listed in the exclusion criteria must be met.
Concomitant Medications											Record medications received within 28 days before the first dose of study intervention through 30 days after the last dose of study intervention, or >30 days for medications for SAEs and ECIs as outlined for AE monitoring timeframe below.
Study Intervention Administration											
Lenvatinib Dispensed	X	X	X	X	X	X					
Lenvatinib Container Returned		X	X	X	X	X	X				
Pembrolizumab Administration	X		X		X						
Tumor Imaging and Efficacy Assessments											
Imaging of chest/abdomen/pelvis and Response Assessment											Baseline imaging should be performed within 28 days before C1. Perform subsequent imaging Q12W (84±7 days) from C1. This schedule will be followed regardless of delays in study intervention. All imaging should be submitted for BICR.

Trial Period	Second Course Treatment Phase Cycle = 42 days						EOT	Posttreatment			Notes
Visit Timing/ Cycle Number	1		2		3 to 9			Safety FU	Efficacy FU	Survival FU	
Cycle Day	1	22	1	22	1	22	At D/C	30 days after D/C	Per Imaging Schedule	Q12W	All procedures/ assessments are to be performed prior to dosing unless otherwise indicated.
Scheduling Window (days)	+3	±3	±3	±3	±3	±3	+7	±7	±7	±14	
Bone Scan											Perform a baseline bone scan within 28 days before C1. Only continue bone scans if participant has positive baseline bone scan. The schedule for on-study bone scans is Q24W (168 ± 7 days). Perform for participants at time of CR if positive at baseline. Schedule should follow calendar days and not be adjusted for delays in treatment.
Brain Scan	X*										*Perform within 28 days before C1 ONLY for participants with previously documented brain metastases (to confirm stability) or who are clinically symptomatic. Brain scans will be performed as clinically indicated and to confirm a CR in participants with brain metastasis at baseline.
Subsequent Anticancer Therapy Status							X	X	X	X	
Survival Status										X	Upon Sponsor request, participants may be contacted for survival status at any time during the course of the study.
Clinical Procedures/Assessments											
Full Physical Examination	X						X				
Directed Physical Examination		X	X	X	X	X		X			
Weight	X	X	X	X	X	X	X	X			
Vital Signs	X	X	X	X	X	X	X	X			HR, DBP, SBP, RR, temperature.

Trial Period	Second Course Treatment Phase Cycle = 42 days						EOT	Posttreatment			Notes
Visit Timing/ Cycle Number	1		2		3 to 9			Safety FU	Efficacy FU	Survival FU	
Cycle Day	1	22	1	22	1	22	At D/C	30 days after D/C	Per Imaging Schedule	Q12W	All procedures/ assessments are to be performed prior to dosing unless otherwise indicated.
Scheduling Window (days)	+3	±3	±3	±3	±3	±3	+7	±7	±7	±14	
ECHO/MUGA	X*						X				*If a previous ECHO/MUGA in the Initial Treatment Phase was performed within 24 weeks prior to C1D1 of the Second Course Treatment Phase, this assessment does not need to be repeated. Additional assessments may be performed as clinically indicated.
12-lead ECG	X				X*		X	X			*After Cycle 1, repeat ECG every other cycle (eg, C3, C5, C7, etc.). For high-risk participants (Section 8.3.3), conduct ECG monitoring every cycle. If lenvatinib is discontinued, ECGs are only required at the EOT and Safety Follow-up visits.
ECOG Performance Status	X		X		X		X	X			
AE/SAE Review									X*		*Report AEs occurring within 30 days after the last dose of study intervention. Report SAEs occurring within 90 days after the last dose of study intervention, or within 30 days after the last dose of study intervention if new anticancer therapy is initiated, whichever is earlier.
Laboratory Procedures/Assessments											
Pregnancy Test – Urine or Serum hCG (WOCBP only)	X	X	X	X	X	X		X			WOCBP require negative test within 24 hours prior to first dose of intervention in the Second Course Treatment Phase. Ongoing pregnancy tests should be conducted as indicated in Appendix 2.
Urine Dipstick Testing (or Urinalysis) for Protein	X	X	X	X	X	X					Urinalysis as clinically indicated. See Section 6.6.2.2 for guidance on testing frequency in cases of elevated protein.
Hematology	X		X		X						
Chemistry	X		X		X						
Lipase and Amylase	X		X		X						

Trial Period	Second Course Treatment Phase Cycle = 42 days						EOT	Posttreatment			Notes
Visit Timing/ Cycle Number	1		2		3 to 9			Safety FU	Efficacy FU	Survival FU	
Cycle Day	1	22	1	22	1	22	At D/C	30 days after D/C	Per Imaging Schedule	Q12W	All procedures/ assessments are to be performed prior to dosing unless otherwise indicated.
Scheduling Window (days)	+3	±3	±3	±3	±3	±3	+7	±7	±7	±14	
PT/INR and aPTT or PTT	X										PTT is acceptable if aPTT cannot be determined. Perform testing as clinically indicated for participants taking anticoagulants.
T3 or FT3, FT4, TSH	X		X		X		X	X			
AE=adverse event; aPTT=activated PTT; BICR=blinded independent central review; C=Cycle; CR=complete response; DBP=diastolic blood pressure; D/C=discontinuation; ECG=electrocardiogram; ECI=event of clinical interest; ECHO=echocardiogram; ECOG=Eastern Cooperative Oncology Group; EOT=end-of-treatment; FT3=free T3; FT4=free thyroxine; FU=follow-up; hCG=human chorionic gonadotropin; HR=heart rate; INR=international normalized ratio; MUGA=multiple gated acquisition scan; PT=prothrombin time; PTT=partial thromboplastin time; Q12W=every 12 weeks; Q24W=every 24 weeks; RR=respiratory rate; SAE=serious adverse event; SBP=systolic blood pressure; T3=triiodothyronine; TSH=thyroid-stimulating hormone; WOCBP=woman of childbearing potential.											

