6.6.1 Immune-Related Events and Dose Modification (Withhold, Treat, Discontinue)

Dose Modification and Toxicity Management for Immune-related AEs Associated with Pembrolizumab

AEs associated with pembrolizumab exposure may represent an immune-related response. These irAEs may occur shortly after the first dose or several months after the last dose of pembrolizumab treatment and may affect more than one body system simultaneously. Therefore, early recognition and initiation of treatment is critical to reduce complications. Based on existing clinical study data, most irAEs were reversible and could be managed with interruptions of pembrolizumab, administration of corticosteroids and/or other supportive care. For suspected irAEs, ensure adequate evaluation to confirm etiology or exclude other causes. Additional procedures or tests such as bronchoscopy, endoscopy, skin biopsy may be included as part of the evaluation. Dose Modification and Toxicity Management Guidelines for irAEs associated with pembrolizumab monotherapy, coformulations, or IO combinations are provided in [Table 6](#).

Table 6 Dose Modification and Toxicity Management Guidelines for Immune-related Adverse Events Associated with Pembrolizumab Monotherapy, Coformulations or IO Combinations

General instructions: 
 Severe and life-threatening irAEs should be treated with IV corticosteroids followed by oral steroids. Other immunosuppressive treatment should begin if the irAEs are not controlled by corticosteroids. Pembrolizumab monotherapy, coformulations or IO combinations must be permanently discontinued if the irAE does not resolve or the corticosteroid dose is not ≤ 10 mg/day within 12 weeks of the last treatment. The corticosteroid taper should begin when the irAE is \leq Grade 1 and continue at least 4 weeks. If pembrolizumab monotherapy, coformulations or IO combinations have been withheld, treatment may resume after the irAE decreased to \leq Grade 1 after corticosteroid taper. 				
irAEs	Toxicity Grade (CTCAE v5.0)	Action With Pembrolizumab Monotherapy, Coformulations or IO Combinations	Corticosteroid and/or Other Therapies	Monitoring and Follow-up

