Hypophysitis	Grade 2	Withhold	
 Administer corticosteroids and initiate hormonal replacements as clinically indicated 	
 Monitor for signs and symptoms of hypophysitis (including hypopituitarism and adrenal insufficiency)
	Grade 3 or 4	Withhold or permanently discontinue ^d		
Hyperthyroidism	Grade 2	Continue	
 Treat with nonselective beta-blockers (eg, propranolol) or thionamides as appropriate 	
 Monitor for signs and symptoms of thyroid disorders
	Grade 3 or 4	Withhold or permanently discontinue ^d		

irAEs	Toxicity Grade (CTCAE v5.0)	Action With Pembrolizumab Monotherapy, Coformulations or IO Combinations	Corticosteroid and/or Other Therapies	Monitoring and Follow-up
Hypothyroidism	Grade 2, 3 or 4	Continue	
 Initiate thyroid replacement hormones (eg, levothyroxine or liothyronine) per standard of care 	
 Monitor for signs and symptoms of thyroid disorders
Nephritis: grading according to increased creatinine or acute kidney injury	Grade 2	Withhold	
 Administer corticosteroids (prednisone 1 to 2 mg/kg or equivalent) followed by taper 	
 Monitor changes of renal function
	Grade 3 or 4	Permanently discontinue		
Neurological Toxicities	Grade 2	Withhold	
 Based on severity of AE administer corticosteroids 	
 Ensure adequate evaluation to confirm etiology and/or exclude other causes
	Grade 3 or 4	Permanently discontinue		
Myocarditis	Grade 1	Withhold	
 Based on severity of AE administer corticosteroids 	
 Ensure adequate evaluation to confirm etiology and/or exclude other causes
	Grade 2, 3 or 4	Permanently discontinue		
Exfoliative Dermatologic Conditions	Suspected SJS, TEN, or DRESS	Withhold	
 Based on severity of AE administer corticosteroids 	
 Ensure adequate evaluation to confirm etiology or exclude other causes
	Confirmed SJS, TEN, or DRESS	Permanently discontinue		

irAEs	Toxicity Grade (CTCAE v5.0)	Action With Pembrolizumab Monotherapy, Coformulations or IO Combinations	Corticosteroid and/or Other Therapies	Monitoring and Follow-up

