8.10.4 Posttreatment Visits

8.10.4.1 Safety Follow-up Visit

The mandatory Safety Follow-up Visit should be conducted approximately 30 days after the last dose of study intervention or before the initiation of a new anticancer treatment, whichever comes first.

Participants who are eligible for retreatment/crossover with pembrolizumab may have up to 2 safety follow-up visits, 1 after the Initial Treatment Phase and 1 after the Second Course Treatment Phase.

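### The Second Course schedule (Table 3) has no hematology, chemistry or lipase/amylase at end of treatment or at the 30-day safety visit, although Table 1 has all three at both

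*Combined protocol and SAP*

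**What the plan says.** Table 3 in Section 1.3.3 governs retreatment. Its hematology, chemistry and "Lipase and Amylase" rows carry marks on Day 1 of Cycle 1, Cycle 2 and Cycles 3 to 9, and nowhere else. The next laboratory rows include "T3 or FT3, FT4, TSH", which is marked on the same Day 1 visits and also at EOT and at Safety Follow-up, the column timed at "30 days after D/C". Vital signs, weight, ECG and ECOG are marked at both closing visits too.

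Table 1 in Section 1.3.1, for the Initial Treatment Phase, marks hematology, chemistry, lipase/amylase and thyroid tests at both EOT and Safety Follow-up.

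The Second Course safety visit is a visit in its own right. Section 8.10.4.1 says that participants eligible for retreatment "may have up to 2 safety follow-up visits, 1 after the Initial Treatment Phase and 1 after the Second Course Treatment Phase", and times the visit at "approximately 30 days after the last dose of study intervention or before the initiation of a new anticancer treatment, whichever comes first". The AE/SAE note in Table 3 reads: "Report AEs occurring within 30 days after the last dose of study intervention".

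**The concern.** The safety visit exists to find harm that appears as treatment ends or soon afterwards. Section 6.6.1 says of immune-related events: "These irAEs may occur shortly after the first dose or several months after the last dose of pembrolizumab treatment". Several of the events in Table 6 of that section are recognised from laboratory values. One row is "Nephritis: grading according to increased creatinine or acute kidney injury"; the liver row is graded by multiples of AST, ALT and bilirubin. Both call for corticosteroids from Grade 2. The potential liver-injury event of clinical interest in Section 8.4.7 is likewise defined by laboratory values alone.

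A participant with a rising creatinine or ALT and no symptoms gives the investigator no cause to order a test. If the panel is not scheduled, the abnormality may be missed during the period in which AEs are to be reported. What is at stake is the safety of Second Course participants and the completeness of their AE record, not the trial's estimates.

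**Working it through.** **Step 1. Compare the cells.** Marks for the safety blood tests at the two closing visits:

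| Row | Table 1 EOT | Table 1 Safety FU | Table 3 EOT | Table 3 Safety FU |
|---|---|---|---|---|
| Hematology | X | X | blank | blank |
| Chemistry | X | X | blank | blank |
| Lipase/amylase | X | X | blank | blank |
| Thyroid | X | X | X | X |

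Four rows are marked at both visits in Table 1 and one in Table 3. Panels absent at these visits: 3 × 2 = 6.

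**Step 2. Check that no mark was lost or shifted.** Table 3 has ten visit columns and a notes column, so a full row has 11 cells. Each of the three rows has 11. The thyroid and ECOG rows also have 11 and fall correctly under EOT and Safety Follow-up. A few other Table 3 rows, such as imaging and concomitant medications, show no marks in the text version, but these three rows are complete.

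**Step 3. Look for text that schedules the panels elsewhere.**

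- Section 8.3.5 refers timing to the schedule of activities. It asks for repeats of clinically significant abnormal values up to 30 days after the last dose, which requires a first abnormal value.
- Section 6.6.2.4 refers liver tests to Sections 1.3.1 and 1.3.3 or to clinical indication.
- Section 8.3.5.1 requires blood count and chemistry review before dosing, which does not reach visits after dosing has ended.
- Appendix 2 (Section 10.2) permits extra tests at the investigator's judgement or where local rules require them, and schedules none.

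**Step 4. Interval from the last scheduled panel to the safety visit.** Inputs: the 42-day cycle (Table 3) and the visit 30 days after the last dose (Section 8.10.4.1). The formula is: days from the last Day 1 panel to the last dose, plus 30.

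- Last dose on Day 1, or pembrolizumab alone: 0 + 30 = about 30 days.
- Lenvatinib stopped on Day 22: 21 + 30 = 51 days.
- Lenvatinib taken to the end of the last cycle: 42 + 30 = 72 days.

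The visit comes sooner if it is brought forward for a new anticancer treatment. Under Table 1 the longest nominal gap between panels is 42 days, and both closing visits have them. Under Table 3 the safety visit has no panel in any of the three cases.

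**The case against.** The best defence is that Table 3 is a lighter schedule by design. It has no Day 8, 15 or 36 visit in Cycle 1, images every 12 weeks from the start, scans bone every 24 weeks and drops the biomarker rows. These participants have already had the drug. Nothing obliges Table 3 to mirror Table 1, and because the other sections defer to the schedule, Table 3 contradicts none of them. This stands in part: the documents do not say whether the omission was deliberate, so a reader who infers a proven clerical error goes further than they allow. But a lighter schedule does not explain keeping thyroid tests, ECG and ECOG at both visits while dropping the panels that grade liver and kidney events.

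Much is also covered already. The safety visit keeps a directed physical examination, vital signs, weight, ECG, ECOG, and pregnancy and thyroid tests. Suspected immune-related events must be evaluated, and a participant who stops for a laboratory toxicity has the abnormal values repeated. If stopping is decided at a Day 1 visit, that day's pre-dose panel may in effect serve as the closing one. This stands, and it narrows the gap to abnormalities that are new and silent.

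Two further inferences should be resisted. A reader might take six as the whole shortfall against Table 1. It is not: Table 1 also has the three panels at Screening and on Cycle 1 Day 15, which Table 3 lacks. Those are outside this point. A reader might also take 72 days, or more with visit windows added, as typical. Lenvatinib is optional in the Second Course (Section 4.1), and Table 1's 42 days is a nominal figure, so the fair comparison is nominal with nominal and the range starts at about 30 days.

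**Conclusion.** The point holds as a small participant-safety gap, best labelled a cheap improvement. Six panels that Table 1 places at the two closing visits are absent from Table 3, and the safety visit falls about 30 to 72 days after the last scheduled panel. The exposure is limited to a new, symptom-free liver, kidney, pancreatic or blood abnormality arising after that panel.

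The range assumes nominal visit days and counts the safety visit from the last dose, as Section 8.10.4.1 does; the Table 3 column counts from discontinuation. The 72-day end further assumes lenvatinib through the whole final cycle. The documents do not give the number of Second Course participants, so no number affected can be stated.

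A reader might infer that the trial's results are at risk. They are not: Section 9.6.1 limits ORR, DOR, PFS, CBR and DCR to responses and progressions before Second Course treatment, and Section 9.6.2 limits the primary safety analyses in the same way.

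**What to change.** In Table 3, mark hematology, chemistry and lipase/amylase at EOT and at Safety Follow-up, as Table 1 does and as Table 3 already does for thyroid tests. If the omission was intended, state the reason in the table notes instead. The lenvatinib rules need no change.

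The cost is three added panels at each of two visits that already take place with a blood draw, so no extra visit is needed. Any amendment needs regulatory and ethics review (Appendix 1), so the six marks are best included in one made for other reasons.
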